6.2.5. Patient Reported Outcomes Assessments

All patients are to complete the FCS Symptoms Two Week Recall at Screening and the FCS Symptoms and diet questionnaire on a daily basis for FCS symptoms/diet (minimum of 4 daily assessments per week) and every 4 weeks for FCS Impacts, and complete the PROMIS Adult Short Form v1.1 (Pain Interference 8a) every 4 weeks, for the duration of the study as outlined in Appendix A. Health-related quality of life (as measured by the PROMIS 29+2 Profile vs. 2.1) and an optional PROMIS[®] Short Form v2.0 – Cognitive Function 4a will be assessed at Baseline, 3 months, 6 months and end of study. Patient-reported global impression of severity (PGIS) will be administered at Baseline and every 4 weeks; the patient-reported global impression of change (PGIC) at 6 months and end of study. Patient-reported global impression of severity and PGIC are administered for purposes of PRO validation and estimation of minimal important difference (MID).

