- The PROMIS Cognitive Function Short Form 4a contains 4 questions to assess patient-perceived cognitive deficits over the past seven days. The cognitive function score will be calculated by summing the values of the response to each question to get a raw score, then converting the raw score to a T-score using the PROMIS scoring manual. A T-score of 50 is the average of the United States general population. Higher cognitive function scores indicate better cognitive functioning. If more than 50% of the questions are missing, the cognitive function score will be considered as missing for the visit. If less than or equal to 50% of the questions are missing, the missing items will be imputed using the average of the non-missing items and rounded to the nearest integer.

The pain interference score, PROPr domain and total scores, and cognitive function score will be summarized by treatment group over time using descriptive statistics. The changes from baseline at the primary analysis time point (average of Weeks 23, 25, 27) and at Month 12 (average of Weeks 51 and 53 for PROPr domain and total scores and cognitive function scores, average of Weeks 49, 51 and 53 for pain interference) will be analyzed using an ANCOVA model with the two randomization stratification factors and treatment group as factors and the corresponding baseline score as a covariate, and will be conducted in the FAS.

In addition to the analyses described above based on the observed data, the missing values will be imputed. The changes from baseline at the primary analysis time point and at Month 12 based on the imputed data will be analyzed using an ANCOVA model with the two randomization stratification

factors and treatment group as factors and the corresponding baseline score as a covariate, and will be conducted in the FAS. The missing values will be imputed as follows:

- For patients with a missing baseline value, their baseline score will be imputed using the average of non-missing data from other patients in the same stratification category. In the event of no observed data for imputation, history of pancreatitis will be used as the only classification factor for the purpose of identifying non-missing data for imputation. Additional factors, such as age and gender may be considered to further classify the imputation categories if supported by data.

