Pain interference	Baseline is defined as the last non-missing assessment on or prior to Day 1. If all pre-dose composite scores are missing, the baseline composite score will be considered as missing. Missing baseline will be imputed using the average of non-missing data from other patients in the same stratification category	Month 6 (Primary analysis time point) - average of Weeks 23, 25, 27 Month 12 -average of Weeks 49, 51 and 53 If all composite scores during the period are missing, the missing Month 6 score will be imputed using the data from the visit that is the closest to Day 169 and within $a \pm 30$ days window, the missing Month 12 data will be imputed using the data from the week that is the closest to the Day 351 and within $a \pm 30$ days window. If 2 or more visits with equal distance, then the average will be used.	 Descriptive statistics of the score, change and percent change at Month 6 and Month 12 in the FAS ANCOVA model of change from baseline with the two stratification factors and treatment group as factors and the corresponding baseline score as a covariate in the FAS

4.11.3.6. The Patient Global Impression of Severity Scale (PGIS) score and Patient Global Impression of Change (PGIC) Score

The PGIS score (scaled None = 0, Mild = 1, Moderate = 2, Severe = 3, and Very severe=4), change from baseline in PGIS, and PGIC score (scaled Much better = 1, A little better= 2, No change = 3, A little worse = 4, and Much worse =5) will be tabulated by severity or change category and by treatment group over time.

Change from baseline in PGIS at the primary time point (average at Weeks 23, 25, 27) and at Month 12 (average of Weeks 51 and 53) will be classified to 2 categories: improved (defined as change from baseline ≤ 0) and not improved (defined as change from baseline ≥ 0). The data will be analyzed using a logistic regression model with the two randomization stratification factors and treatment group as factors and baseline PGIS score as a covariate, and will be conducted in the FAS.

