PGIC score at the primary time point (average at Weeks 23, 25, 27) and at Month 12 (average of Weeks 51 and 53) will be classified to 2 categories: improved (defined as PGIC score = Much better [< 1.5] or A little better [1.5 to < 2.5]) and not improved (PGIC score = No change [2.5 to < 3.5], A little worse [3.5 to < 4.5], Much worse [\geq 4.5]) and analyzed using a logistic regression model with the two randomization stratification factors and treatment group as factors and baseline PGIS score as a covariate, and will be conducted in the FAS.

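### Patient global ratings (PGIC, PGIS) are compared between arms only after a cut to improved / not improved; for PGIC the cut could cost about 10 to 22 points of power if the true shift is 0.6 to 1.0 SD

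*Combined protocol and SAP*

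**What the plan says.** SAP 4.11.3.6 scores PGIS from 0 to 4 and PGIC from 1 to 5. It uses them in two ways.

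- **Description.** PGIS, its change from baseline and PGIC "will be tabulated by severity or change category and by treatment group over time". No treatment comparison is attached to these tables.
- **Comparison of arms.** For PGIS the quantity is "Change from baseline in PGIS at the primary time point (average at Weeks 23, 25, 27", with Weeks 51 and 53 averaged for Month 12. It is then split into "improved (defined as change from baseline ≤ 0) and not improved (defined as change from baseline ≥ 0". PGIC is averaged over the same visits. Its improved class is "improved (defined as PGIC score = Much better [< 1.5] or A little better [1.5 to < 2.5", and every average of 2.5 or more is not improved. For PGIS, "The data will be analyzed using a logistic regression model with the two randomization stratification factors and treatment group as factors and baseline PGIS score"; the last of these enters as the covariate. The PGIC model has the same terms.

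Elsewhere the SAP keeps the score whole. For the PROMIS measures (SAP 4.11.3.5), change from baseline "will be analyzed using an ANCOVA model with the two randomization stratification factors and treatment group as factors". FCS symptoms (4.11.3.3) and FCS Impacts (4.11.3.4) are handled the same way.

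On the purpose of the two global scales, protocol 6.2.5 says that PGIS and "PGIC are administered for purposes of PRO validation and estimation of minimal important difference (MID".

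**The concern.** No ordinal or continuous comparison of PGIC or PGIS between arms appears in the protocol or the SAP. The only test is on the two-class version, and SAP 4.11.3.6 gives no reason for treating these scales differently from its other patient-reported scores. The PGIC cut puts *much better* with *a little better*, and *no change* with *much worse*. With about 20 patients per arm there is little information to spare, so a real shift in patients' overall rating is more likely to be missed than under the method the SAP already uses next door. At stake is the sensitivity of an exploratory comparison, not any confirmatory conclusion.

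**Working it through.** **Inputs from the documents.** Two-sided 5% tests (SAP 4.2.1). Planned size 60: two cohorts of 30, each split 2:1, gives 20 on 50 mg, 20 on 80 mg and 10 + 10 = 20 on pooled placebo. The lay summary of results gives 22 (80 mg), 21 (50 mg) and 23 (placebo). No effect size, SD, response rate or power is stated for PGIC or PGIS, so those below are assumptions.

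**Calibration.** The only stated power is for triglycerides (SAP 4.12): 14 per group, difference 60, SD 46, 90%. Noncentral t: 60/46 ÷ √(1/14 + 1/14) = 3.45 on 26 df, power 91.3%. This agrees with the plan to within 2 points, so the same formula is used below.

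**What the cut removes.** The mean of three PGIC visits is a sum from 3 to 15 divided by 3, which gives 13 possible values. The mean of two visits has 9 (sums 2 to 10). The cut leaves 2. Ratings of 3, 3, 3 (*no change* throughout) fall in the same class as 5, 5, 5 (*much worse* throughout). Averaging reduces visit-to-visit noise and is not where the loss arises.

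**Closed form.** Take 20 per arm, a normal score and a true difference of d SDs of that score. Uncut power comes from the noncentral t with parameter d/√(1/20 + 1/20) on 38 df. For the cut score, with placebo improved rate p0, the active rate is p1 = Φ(Φ⁻¹(p0) + d), and a two-proportion normal approximation is used.

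Example, d = 0.8 and p0 = 0.30:
- Uncut: 0.8 × 3.162 = 2.53, critical value 2.024, power 69.3%.
- Cut: p1 = Φ(−0.524 + 0.8) = 0.609. Pooled rate 0.454, null SE √(0.454 × 0.546 × 0.1) = 0.157, alternative SE √(0.30 × 0.70/20 + 0.609 × 0.391/20) = 0.150. Power = Φ((0.309 − 1.96 × 0.157)/0.150) ≈ Φ(0) = 50.0%.
- Loss: 19.3 points.

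Over assumed placebo improved rates of 20% to 50%:

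| d | Uncut power | Points lost |
|---|---|---|
| 0.2 | 9.5% | 2–3 |
| 0.4 | 23% | 7–9 |
| 0.6 | 46% | 14–17 |
| 0.8 | 69% | 19–22 |
| 1.0 | 87% | 18–23 |
| 1.2 | 96% | 12–19 |
| 1.5 | 99.6% | 3–11 |

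**Simulation of PGIC.** Five categories were cut from a latent normal score and averaged over three visits, with between-visit correlation 0.5 or 0.8. Placebo distributions were 10/20/45/15/10, 5/15/60/15/5 and 15/30/40/10/5 percent. The shift is in SDs of the latent single-visit score.

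Two arms of 20, ANCOVA on the average against the logistic Wald test on the cut, 3,000 trials per setting:

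| Shift | Cut | Uncut | Points lost |
|---|---|---|---|
| 0.6 | 29–41% | 46–57% | 13–21 |
| 0.8 | 49–65% | 70–82% | 16–22 |
| 1.0 | 67–81% | 87–95% | 13–22 |

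Type I error was 4–5% for ANCOVA and 2–6% for the logistic test.

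The SAP's three-arm model at 22/21/23, with both strata and baseline PGIS:
- Against the Wald test the loss was 1–4 points at shift 0.2 and 5–13 at 0.4.
- Against the likelihood-ratio test it was 0–1 at 0.2, 4–8 at 0.4, 13–17 at 0.6, 15–18 at 0.8 and 8–16 at 1.0.
- A separate run of this model, taking both tests together, gave 10–22 points at 0.6 to 1.0 and 0–8 at 0.3.

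**PGIS.** Under one assumed distribution (15/30/35/15/5 percent, correlation 0.5 or 0.7) and with baseline adjustment, the loss was 8–16 points at shift 0.3 and 21–41 at 0.5 to 0.7, a different range from PGIC. The handling of zero matters too. In the simulated placebo arm, 39–42% were improved when the cut was below zero and 57–59% when zero was included, so 15 to 20 points of the placebo arm (57 − 42 and 59 − 39) lay at exactly zero.

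**The case against.** **Low stakes.** These analyses sit under SAP 4.11.3, Additional/Exploratory Analysis, outside the 28-step testing sequence in SAP 4.9.1.3. Protocol 6.2.5 presents the scales as tools for validation and for estimating a minimal important difference. No confirmatory claim rests on their power. This stands and limits the point to a cheap improvement.

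**Assumed effects.** The size of the loss depends on shifts that the documents do not supply. This also stands. Both ends of the range must be shown, and the upper figures hold only for moderate to large shifts.

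**The Wald test.** Part of the gap reflects a conservative Wald test, which SAP 4.11.3.6 does not prescribe. A likelihood-ratio test usually recovers 2 to 5 points, with type I error up to 6.8% in some settings. Most of the loss at 0.6 to 1.0 SD remains.

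**Scale type.** PGIC and PGIS are single five-level items, unlike the 0–10 scales, composites and T-scores that the SAP analyses by ANCOVA. ANCOVA treats the steps as equally spaced. That is a fair reservation, and a proportional-odds model answers it without cutting.

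**Worsening.** A reader might infer that worsening on placebo disappears from the report. It does not: the category tables by arm and time keep it visible. It is only not tested.

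**Conclusion.** The point holds as an improvement to an exploratory analysis. The cut discards information that the averaged scores contain. For PGIC at about 20 patients per arm, assuming a latent shift of 0.6 to 1.0 SD, it costs about 10 to 22 points of power; the lowest single figure was 8, with a likelihood-ratio test at 1.0 SD. For shifts of 0.4 SD or less the loss is about 0 to 9 points, except that the Wald test lost up to 13 at 0.4 SD. In the closed form the loss shrinks again beyond about 1.2 SD.

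Three stronger readings are not supported:
- That one loss figure applies to both scales. The range was computed for PGIC. For PGIS the test is not defined as printed, because a change of exactly zero meets both conditions. That may be a fault of text extraction and should be checked against the signed SAP.
- That averaging over visits is part of the cost. It reduces noise, and the fix keeps it.
- That the trial's case for patient benefit is weakened. The scales are exploratory and were included for validation.

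**What to change.** In SAP 4.11.3.6, make the main between-arm analysis at Month 6 and Month 12 an ANCOVA of the averaged PGIC score, and of the change from baseline in averaged PGIS. Use treatment group, the two stratification factors and baseline PGIS, all already listed there. If equal spacing of the categories is doubted, a proportional-odds model with the same terms is an acceptable alternative. Keep the improved / not improved table and the logistic regression as supportive. Check the PGIS class limits and state in which class a change of zero falls.

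The cost is a wording change in one exploratory section, following the model already specified for PROMIS and FCS Impacts. It needs no new data and does not touch the confirmatory sequence. The downside is that a difference in mean category is less intuitive than a responder percentage, which is why the responder table stays.

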4.11.3.7. Diet Questions

Responses to daily dietary questions will be listed.

4.11.3.8. Number of ER Visits, Incidence of All-cause Hospitalization, and Number of In-patient Days

The yearly rate of ER visits, all-cause hospitalization, and in-patient days during the treatment period will be summarized using descriptive statistics. The yearly rates for each patient will be calculated as number of ER visits, incidence of all-cause hospitalization, or number of in-patient days times 365.25 divided by number of days during the treatment period.

If supported by data, the number of ER visits and incidence of all-cause hospitalization during the treatment period may be compared between pooled ISIS 678354 treatment group and placebo group using a Negative Binomial regression model in the FAS. The model will include the treatment group and the 2 stratification factors as the factors. The logarithm of time in year that each patient observed during the Treatment Period will be used as an offset variable.

The yearly rate of in-patient days may be compared between pooled ISIS 678354 treatment group and placebo group using an ANCOVA model with the treatment group and the 2 stratification factors as the factors, and will be conducted in the FAS.

4.12. Determination of Sample Size

Based upon prior clinical trial experience with FCS patients, the SD of the percent change from Baseline in TGs is approximately 46%. With 14 patients in each ISIS 678354 treatment group and 14 in the pooled placebo group, there would be a 90% power to detect a 60% difference between each ISIS 678354 treatment group and pooled placebo group at an alpha level of 0.05 (two-sided), assuming 60% reduction in the ISIS 678354 treatment patients and no change in the placebo patients. Approximately 60 patients will be enrolled in this trial to account for potential early dropouts and to facilitate general safety evaluation.

Eligible patients will be randomized 1:1 to Cohort A or Cohort B and each cohort further randomized 2:1 (ISIS 678354:placebo) and stratified for:

- Prior history of pancreatitis within 10 years prior to Screening* vs. no history of pancreatitis or no history within 10 years prior to Screening
- Previous treatment with volanesorsen
- * History of pancreatitis is defined as a recorded diagnosis of acute pancreatitis or hospitalization for severe abdominal pain consistent with acute pancreatitis and for which no alternate diagnosis was made

